#### **6.6.14. Recording of AEs, SAEs, pregnancies and pIMDs**

- Refer to Section [9.3](#) for procedures for the investigator to record AEs, SAEs, pregnancies and pIMDs. Refer to Section [9.4](#) for guidelines and how to report SAE, pregnancy and pIMD reports to GSK Biologicals.
- The subjects /subject's LAR(s)/caregiver will be instructed to contact the investigator immediately should they manifest any signs or symptoms they perceive as serious.
- At each vaccination visit, diary cards will be provided to the subject/subject's LAR/caregiver. The subject will be instructed to measure and record the oral body temperature and any solicited local/general AEs (that is, on the day of vaccination and during the next 6 days) or any unsolicited AEs (that is, on the day of vaccination and during the next 29 days occurring after vaccination). The subject will be instructed to return the completed diary card to the investigator at the next study visit.
- Any unreturned diary cards will be sought from the subject through telephone call(s) or any other convenient method.
- The investigator will transcribe the collected information into the eCRF in English.

### **6.6.15. Monthly contact**

After Visit 3 (Month 3), all subjects will be contacted by the study staff on a monthly basis until the study end (that is, until all the subjects complete their last contact, occurring within 30 days of the projected study conclusion date of the last enrolled subject, that is, 26 months [790 days] from the enrolment date). Therefore, duration of the follow-up will vary for each subject and subjects enrolled early in the trial could be followed for longer duration than the subjects who enrol later in the trial.

### **6.6.16. Study conclusion**

Study conclusion will be scheduled based on the projected date of the last contact of the last enrolled subject, that is, 26 months (790 days) from the enrolment date. All sites will be notified of this date as to schedule the study conclusion contact for all subjects within 30 days of that date.

The study conclusion visit/ contact for subjects with an ongoing episode of HZ will occur after a 4-week pain-free period is documented OR after Day HZ-92 follow-up has been completed (see [Table 8](#)).

At the study conclusion contact the investigator will:

- review data collected to ensure accuracy and completeness,
- complete the Study Conclusion screen in the eCRF.

After study conclusion, placebo recipients may be offered cross-over vaccination with HZ/su, if supported by study results.

## **6.7. *Study procedures during special circumstances (Amended 14 April 2020)***

*During special circumstances (e.g., COVID-19 pandemic), the specific guidance from local public health and other competent authorities regarding the protection of individuals' welfare must be applied. For the duration of such special circumstances, the following measures may be implemented for enrolled subjects:*

*The impact of COVID-19 to the study conduct will be documented in the clinical study report.*

- *Safety follow-up may be made by a telephone call, other means of virtual contact or home visit, if appropriate.*
- *Diary cards may be transmitted from and to the site by electronic means and/or conventional mail.*
- *Biological samples may be collected at a different location\* other than the study site or at subject's home. Biological samples should not be collected if they cannot be processed in a timely manner or appropriately stored until the intended use.*

*\* It is the investigator's responsibility to identify an alternate location. The investigator should ensure that this alternate location meets ICH GCP requirements, such as adequate facilities to perform study procedures, appropriate training of the staff and documented delegation of responsibilities in this location. This alternate location should be covered by proper insurance for the conduct of study on subjects by investigator and staff at a site other than the designated study site. Refer to EMA Guidance on the Management of Clinical Trials during the COVID-19 (Coronavirus) pandemic (version 2, 27 March, 2020) for more details.*

- *If despite best efforts it is not possible to collect the biological samples within the interval predefined in the protocol (see Table 9), then the interval may be extended as outlined in Table 11.*
- *If despite best efforts it is not possible to administer the second dose of study intervention as defined in the protocol (see Table 9), a maximum dose interval of 180 days may be used (see Table 11).*
  - *In case the investigator needs to conduct visits 2 and 3 during the allowed extended interval due to the special circumstances, then the best efforts should be made to conduct a safety follow-up by telephone contact at the time when visits 2 and 3 were initially planned (as close to the optimal window as possible) and approximately monthly thereafter until visits 2 and 3 procedures can be conducted.*

**Table 11      Intervals between study visits during special circumstances  
(Amended 14 April 2020)**

Interval	Optimal length of interval	Allowed interval per Protocol	Allowed interval during special circumstances
Visit 1 → Visit 2	60 days (2 months)	49 days - 83 days	49 days – 180 days
Visit 2 → Visit 3	30 days (1 month)	28 days- 48 days	28 days- 90 days
Between Monthly Contacts*	30 days (1 month)	20 – 40 days	20 – 40 days
Visit 2 → Month 26 Contact (for the last enrolled subject only)	730 days (24 months)	730- 760 days	730- 760 days

*Note: Investigator should prioritize conducting the visit as close to the optimal window as possible.*

- *Visits for suspected HZ may take place in a different location\* other than the study site or at subject's home. If this is not feasible, then the medical evaluation of suspected HZ may take place virtually with documentation of all the signs and symptoms as outlined in Table 8 and Table 10.*
  - *If the subject is not able to contact the study staff/investigator to evaluate/clinically diagnose the suspected HZ case, the subject should be encouraged to document all the signs and symptoms and record the progression of the rash and share it with the investigator when possible.*

- *Digital photographs can be taken by the study staff/investigator at a different location\* other than the study site or at subject's home. If this is not feasible, subjects might be asked to take photographs of their Hz lesions themselves. The photographs will be transferred to the investigator.*
- *ZBPI questionnaire may be transmitted from and to the site by electronic means and/or conventional mail. If feasible the study staff/investigator can conduct ZBPI questionnaire by telephone contact.*

*Impact on the modified exposed set for HZ recurrence analysis and per protocol set for immunogenicity (humoral and ~~CCI~~ ) will be determined on a case by case basis.*

## 6.8. Biological sample handling and analysis

Please refer to the central lab manual for details on biospecimen management (handling, storage and shipment).

Samples will not be labelled with information that directly identifies the subject but will be coded with the identification number for the subject (subject number).

- Collected samples will be used for protocol mandated research and purposes related to the improvement, development and quality assurance of the laboratory tests described in this protocol. This may include the management of the quality of these tests, the maintenance or improvement of these tests, the development of new test methods, as well as making sure that new tests are comparable to previous methods and work reliably.
- It is also possible that future findings may make it desirable to use the samples acquired in this study for future research, not described in this protocol. Therefore, all subjects in countries where this is allowed will be asked to give a specific consent to allow GSK or a contracted partner to use the samples for future research. Future research will be subject to the laws and regulations in the respective countries and will only be performed once an independent Ethics Committee or Review Board has approved this research.

Information on further investigations and their rationale can be obtained from GSK Biologicals.

If additional testing is performed, the marker priority ranking given in Section 6.8.4 may be changed.

Any sample testing will be done in line with the consent of the individual subject/subject's LAR(s).

Refer also to the [Investigator Agreement](#), where it is noted that the investigator cannot perform any other biological assays except those described in the protocol or its amendment(s).

Collected samples will be stored for a maximum of 20 years (counting from when the last subject performed the last study visit), unless local rules, regulations or guidelines require different timeframes or different procedures, which will then be in line with the subject consent. These extra requirements need to be communicated formally to and discussed and agreed with GSK Biologicals.

### 6.8.1. Use of specified study materials

When materials are provided by GSK Biologicals, it is MANDATORY that all clinical samples (including serum samples) be collected and stored exclusively using those materials in the appropriate manner. The use of other materials could result in the exclusion of the subject from the per-protocol analysis (See Section 11.5 for the definition of cohorts to be analyzed). The investigator must ensure that his/her personnel and the laboratory(ies) under his/her supervision comply with this requirement. However, when GSK Biologicals does not provide material for collecting and storing clinical samples, appropriate materials from the investigator's site must be used. Refer to the Module on Clinical Trial Supplies in the SPM.

### 6.8.2. Biological samples

The biological samples collected in the study, the quantity needed, the unit and the time points are described in Table 12.

**Table 12 Biological samples**

Sample type	Quantity	Unit	Timepoint	Sub-set name*
Blood-Humoral	approx 5	ml	scheduled	All subjects
CCI				
HZ lesion sample	preferably 3 samples	-	unscheduled	All subjects with suspected HZ episodes during the study

\*Refer to Section 5.1 for sub-cohort description

Approx= Approximately; CCI HZ= Herpes Zoster; ml= milliliter

### 6.8.3. Laboratory assays

Please refer to APPENDICES

APPENDIX A for a detailed description of the assays performed in the study. Please refer to APPENDIX B for the address of the clinical laboratories used for sample analysis.

[figure not shown]
Laboratory assays which will be used in this study are summarised in **Table 13** (Humoral Immunogenicity), **Table 14** CCI and **Table 15** (Molecular Biology), respectively.

**Table 13      Humoral Immunity (Antibody determination)**

System	Component	Method	Kit /Manufacturer	Unit*	Cut-off	Laboratory
SERUM	Varicella Zoster Virus Glycoprotein E Ab. IgG	ELISA	NA	mIU/mL	97	GSK Biologicals

Ab: Antibody; ELISA: Enzyme-linked Immunosorbent Assay; IgG: Immunoglobulin class G; mIU: milli-international unit; ml= milliliter; NA: Not applicable

CCI

**Table 15      Molecular Biology (PCR tests)**

System	Component	Method	Unit	Laboratory
HZ lesion sample	Varicella Zoster Virus DNA	PCR	No unit	GSK Biologicals
HZ lesion sample	Actin Gene DNA	PCR	No unit	GSK Biologicals

DNA= Deoxyribonucleic Acid; HZ= Herpes Zoster; PCR= Polymerase Chain Reaction

Additional exploratory testing on the vaccine and/or on the disease under study may be performed within the framework of the study if deemed necessary for accurate interpretation of the data or should such assay(s) become available at GSK. These assays may not be represented in the objectives/endpoints of the study protocol.

The GSK Biologicals'/contract research organization's (CRO) clinical laboratories have established a Quality System supported by procedures. The activities of GSK Biologicals'/CRO's clinical laboratories are audited regularly for quality assessment by an internal (sponsor-dependent) but laboratory-independent Quality Department. Clinical laboratories contracted by GSK also conform to Good Laboratory Practice guidelines and operate in compliance with regulatory standards.

## 6.8.4. Biological samples evaluation

### 6.8.4.1. Immunological read-outs

The plan for immunogenicity testing on samples obtained is shown in [Table 16](#)

**Table 16 Immunological read-outs**

Blood sampling timepoint		Sub-cohort Name	Number of targeted subjects	Component
Type of contact and timepoint	Sampling timepoint			
Day 1 (Visit 1)	Pre-vacc 1	All subjects CCI	1426	Ab gE ELISA
Month 2 (Visit 2)	Pre-vacc 2	All subjects CCI	1426	Ab gE ELISA
Month 3 (Visit 3)	Post-vacc 2	All subjects CCI	1426	Ab gE ELISA

Ab: Antibody; CCI: [REDACTED] ELISA: Enzyme-linked Immunosorbent Assay; gE: recombinant purified Glycoprotein E; CCI: [REDACTED]; Pre-Vacc: pre-vaccination; Post-Vacc: post-vaccination;

## 6.8.5. Immunological correlates of protection

No generally accepted immunological correlate of protection against HZ has been demonstrated so far for the gE antigen used in the HZ/su study vaccine.

## 7. STUDY VACCINES AND ADMINISTRATION

### 7.1. Description of study vaccine

The study vaccine to be used has been developed and manufactured by GSK Biologicals.

The Quality Control Standards and Requirements for the vaccine are described in separate Quality Assurance documents (e.g. release protocols, certificate of analysis) and the required approvals have been obtained.

The vaccine/placebo are labelled and packed according to applicable regulatory requirements.

Commercial vaccines are assumed to comply with the specifications given in the manufacturer's Summary of Product Characteristics.

**Table 17 Study vaccine and Placebo**

Treatment name	Vaccine name	Formulation	Presentation	Volume to be administered	Number of doses
HZ/su	VZV gE	gE=50µg (50µg gE per 0.5ml of reconstituted vaccine)	Lyophilized pellet in a monodose vial	0.5 ml	2
	AS01B	MPL=50µg; QS21=50µg; Liposomes per 0.5 ml of reconstituted vaccine	Liquid in a monodose vial		
Placebo	Lyophilised sucrose	Sucrose=20mg (20mg sucrose per 0.5ml of reconstituted placebo)	Lyophilized pellet in a monodose vial	0.5 ml	2
	Saline (NaCl) solution	NaCl=150mM (150mM NaCl solution [salt water for injection])	Liquid in a monodose vial		

AS01B= Adjuvant System 01B; gE= recombinant purified Glycoprotein E; MPL= 3-O-desacyl-4'-monophosphoryl lipid A; NaCl= Sodium Chloride; QS21: Quillaja saponaria Molina, fraction 21 (Licensed by GSK from Antigenics Inc, a wholly owned subsidiary of Agenus Inc., a Delaware, USA corporation)

### 7.2. Storage and handling of study vaccines

The study vaccine must be stored at the respective label storage temperature conditions in a safe and locked place. Access to the storage space should be limited to authorized study personnel. The storage conditions will be assessed during pre-study activities under the responsibility of the sponsor study contact. The storage temperature should be continuously monitored with calibrated (if not validated) temperature monitoring device(s) and recorded. Refer to the Module on Clinical Trial Supplies in the SPM for more details on storage of the study vaccine.

Temperature excursions must be reported in degree Celsius.

Any temperature excursion outside the range of 0.0 to +8.0°C (for +2 to +8°C/+36 to +46°F label storage condition) impacting investigational medicinal products (IMPs) must be reported in the appropriate (electronic) temperature excursion decision form ([e]TDF).

The impacted IMPs must not be used and must be stored in quarantine at label temperature conditions until usage approval has been obtained from the sponsor.

In case of temperature excursion below +2.0°C down to 0.0°C impacting IMP(s) there is no need to report in (e)TDF, but adequate actions must be taken to restore the +2 to +8°C/+36 to +46°F label storage temperature conditions. The impacted IMP(s) may still be administered, but the site should avoid re-occurrence of such temperature excursion. Refer to the Module on Clinical Trial Supplies in the SPM for more details on actions to take.

Refer to the Module on Clinical Trial Supplies in the SPM for details and instructions on the temperature excursion reporting and usage decision process, packaging and accountability of the study vaccines.

### 7.3. Dosage and administration of study vaccine/placebo

After removal of the vaccine components from the temperature monitored refrigerator, the vaccine should be reconstituted and administered within 6 hours, and should be kept at room temperature (not to exceed the range of 2°C/36°F and 30°C/86°F).

Vaccine will be administered as indicated in [Table 18](#).

The reconstituted vaccine (0.5 ml) should be administered by intra-muscular (IM) injection into the deltoid muscle of the non-dominant arm using a standard aseptic technique.

Refer to the SPM for more details on vaccine reconstitution and administration.

**Table 18 Dosage and administration**

Type of contact and timepoint	Volume to be administered	Study group	Treatment name	Route	Site	Side 
Visit 1 (Day 1)	0.5 ml	HZ/su	HZ/su	IM	Deltoid	Non-dominant
Visit 2 (Month 2)						
Visit 1 (Day 1)	0.5 ml	Placebo	Placebo			
Visit 2 (Month 2)						

IM: Intramuscular; ml= milliliter

 The non-dominant arm is the preferred arm of injection. In case it is not possible to administer the vaccine in the non-dominant arm, an injection in the dominant arm may be performed.

### 7.4. Replacement of unusable vaccine doses

In addition to the vaccine doses provided for the planned number of subjects (including over-randomization when applicable), at least 5% additional vaccine doses will be supplied to replace those that are unusable.

## 7.5. Contraindications to subsequent vaccination

The following events constitute absolute contraindications to further administration of study vaccine. If any of these events occur during the study, the subject must not receive additional doses of vaccine but may continue other study procedures at the discretion of the investigator (see Section 9.5).

- Anaphylaxis following the administration of vaccine
- Pregnancy (see Section 9.2.1)
- Any SAE judged to be vaccine-related by the investigator.
- Occurrence of HZ between the first and second vaccine dose.
- Any confirmed or suspected immunosuppressive or immunodeficient condition, including Human Immunodeficiency Virus (HIV) infection.
- Any condition that in the judgment of the investigator would make intramuscular injection unsafe.
- Occurrence of a new pIMD or the exacerbation of an existing pIMD that, in the opinion of the investigator, expose the subject to unacceptable risk from subsequent vaccination. In such cases, the investigator should use his/her clinical judgement prior to administering the next dose of the vaccine. Refer to Section 9.1.5.1 for the definition of pIMDs.

The following events constitute contraindications to administration of study vaccine at that point in time; if any of these events occur at the time scheduled for vaccination, the subject may be vaccinated at a later date, within the time window specified in the protocol (see Section 6.5), or the subject may be withdrawn from vaccination at the discretion of the investigator (see Section 9.5).

- Acute disease and/or fever at the time of vaccination.
  - Fever is defined as temperature  $\geq 38.0^{\circ}\text{C} / 100.4^{\circ}\text{F}$ . The preferred location for measuring temperature in this study will be the oral cavity.
  - Subjects with a minor illness (such as mild diarrhoea, mild upper respiratory infection) without fever can be administered study vaccines.

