### 11.2. Secondary endpoints

[figure not shown]
- Occurrence of confirmed HZ episodes from first study vaccination until study end.
- Reactogenicity and safety, in all subjects
  - Occurrence, intensity and duration of each solicited local AE within 7 days (Days 1-7) after each vaccination.
  - Occurrence, intensity, duration and relationship to vaccination of each solicited general AE within 7 days (Days 1-7) after each vaccination.
  - Occurrence, intensity, duration and relationship to vaccination of unsolicited AEs within 30 days (Days 1-30) after each vaccination, according to the Medical Dictionary for Regulatory Activities (MedDRA) classification.
  - Occurrence and relationship to vaccination of all SAEs from dose 1 up to 30 days post last vaccination.
  - Occurrence and relationship to vaccination of any pIMDs from dose 1 up to 30 days post last vaccination.
  - Occurrence and relationship to vaccination of all SAEs within the period starting after 30 days post last vaccination until 1 year post last vaccination.
  - Occurrence and relationship to vaccination of any pIMDs within the period starting after 30 days post last vaccination until 1 year post last vaccination.
  - Occurrence of SAEs related to investigational vaccine, related to study participation or to GSK concomitant medication/vaccine during the entire study period.
- Immunogenicity, in all subjects
  - Vaccine response for anti-gE humoral immunogenicity as determined by ELISA at Month 2 and Month 3.
  - Anti-gE antibody concentrations as determined by ELISA at Day 1, Month 2 and Month 3.

CCI

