- All pIMDs and related pIMDs occurring from first vaccination up to 30 days post last vaccination will be tabulated.
- All pIMDs and related pIMDs occurring after 30 days post last vaccination until 1 year post last vaccination will be tabulated.
- All SAEs, related SAEs occurring from first vaccination up to 30 days post last vaccination will be tabulated.

- All SAEs, related SAEs occurring after 30 days post last vaccination until one year post last vaccination will be tabulated.
- Fatal SAEs will be tabulated using date of onset of SAE in the following manner – within Day 1-Month 3 (30 days post last vaccination), Day 1 to Month 14 (one year post last vaccination) and Month 3 till study end. Fatal SAEs will also be tabulated using the date of death within the same time periods.
- All SAE related to investigational vaccine, related to study participation or to GSK concomitant medication/vaccine occurring during the entire study period will be tabulated.
- AEs/SAEs leading to withdrawal from the study will be tabulated.

CCI

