- All pIMDs and related pIMDs occurring from first vaccination up to 30 days post last vaccination will be tabulated.
- All pIMDs and related pIMDs occurring after 30 days post last vaccination until 1 year post last vaccination will be tabulated.
- All SAEs, related SAEs occurring from first vaccination up to 30 days post last vaccination will be tabulated.
- All SAEs, related SAEs occurring after 30 days post last vaccination until one year post last vaccination will be tabulated.
- Fatal SAEs will be tabulated using date of onset of SAE in the following manner – within Day 1-Month 3 (30 days post last vaccination), Day 1 to Month 14 (one year post last vaccination) and during the entire study period. Fatal SAEs will also be tabulated using the date of death within the same time periods.
- All SAE related to investigational vaccine, related to study participation or to GSK concomitant medication/vaccine occurring during the entire study period will be tabulated.
- AEs/SAEs leading to withdrawal from the study will be tabulated.

CCI

- [REDACTED]
- [REDACTED]
- [REDACTED]

CCI

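### Read literally, the early SAE and pIMD window ends 30 days after the last dose received, so a vaccine-related SAE or unacceptable-risk pIMD that stops dose 2 can move itself into the late table

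*Protocol*

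**What the plan says.** **The windows.** Protocol 11.2 defines the early SAE endpoint as "Occurrence and relationship to vaccination of all SAEs from dose 1 up to 30 days post last vaccination" and the early pIMD endpoint as "Occurrence and relationship to vaccination of any pIMDs from dose 1 up to 30 days post last vaccination". The late SAE endpoint is "Occurrence and relationship to vaccination of all SAEs within the period starting after 30 days post last vaccination until 1 year post last vaccination", and the late pIMD endpoint has the same form. SAP 5.5.1 carries the split into the tables: "All SAEs, related SAEs occurring from first vaccination up to 30 days post last vaccination will be tabulated".

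**The stopping rule.** Protocol 7.5 lists among its absolute contraindications "Any SAE judged to be vaccine-related by the investigator". It also lists a new or worsened pIMD that would, in the investigator's opinion, "expose the subject to unacceptable risk from subsequent vaccination". After either event, "the subject must not receive additional doses of vaccine but may continue other study procedures at the discretion of the investigator". Protocol 10.2.2 confirms that stopping vaccination does not in itself mean leaving the study. These subjects also stay in the Exposed Set, on which safety is analysed.

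**The boundary as a calendar point.** For fatal SAEs, Protocol 11.10 gives the windows as "within Day 1-Month 3 (30 days post last vaccination), Day 1 to Month 14 (one year post last vaccination"), and SAP 5.5.1 uses the same labels. Protocol 7.7.1 places the 30-day point at Day 90. Protocol Table 22 places it at Visit 3 (Month 3), and the one-year point at Month 14.

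Neither document says what the last vaccination is, for these windows, in a subject who never receives dose 2.

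**The concern.** If the last vaccination is the last dose received, an event that stops dose 2 makes dose 1 the last dose and so fixes its own window. A related SAE on Day 45 closes the early window at Day 30, after the fact, and is then counted as late. An unrelated SAE on Day 45 in a subject who receives dose 2 on Day 60 is counted as early. The split therefore depends on something that happens after the event starts and that the event itself influences.

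The direction is not neutral. Within Days 31–60, the events that leave the early table are those judged related, or the pIMDs judged to carry unacceptable risk. The effect is larger in whichever arm has more of them. Early counts would be understated and late counts overstated for named secondary endpoints. pIMDs are the protocol's adverse events of specific interest (Protocol 9.1.5.1).

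Other reasons for missing dose 2 in Protocol 7.5, such as HZ between doses, shorten the early window in the same way for any SAE in those subjects.

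**Working it through.** **Inputs.** Dose 1 to dose 2: optimal 60 days, allowed 49–83 days (Protocol Table 9), up to 180 days in special circumstances (Protocol 6.7 and Table 11). Early window end: last dose + 30 days. Late window end: last dose + 1 year. Days are counted from dose 1.

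**Step 1: the plan's own figure.** Dose 2 on the optimal day gives 60 + 30 = Day 90, as in Protocol 7.7.1. The calendar label is therefore exact for a two-dose subject on the optimal schedule.

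**Step 2: one-dose subject, literal reading.** 0 + 30 = Day 30, so the early window is 30 days long instead of 90.

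**Step 3: the affected stretch.** An event that stops dose 2 must start before dose 2 would have been given. It leaves the early table if it starts after Day 30. Affected days = interval − 30.

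| Interval (days) | Two-dose early window ends | Affected days | Share of inter-dose days | Share of two-dose early window |
|---|---|---|---|---|
| 49 | Day 79 | 19 | 19/49 = 39% | 19/79 = 24% |
| 60 | Day 90 | 30 | 30/60 = 50% | 30/90 = 33% |
| 83 | Day 113 | 53 | 53/83 = 64% | 53/113 = 47% |
| 180 | Day 210 | 150 | 150/180 = 83% | 150/210 = 71% |

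**Step 4: the same day, two subjects (60-day schedule).**

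| SAE starts | Dose 2 given on Day 60 | Dose 2 stopped |
|---|---|---|
| Day 20 | early | early |
| Day 31 | early | late |
| Day 45 | early | late |
| Day 60 (before dose 2) | early | late |

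Events up to Day 30 are unaffected.

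**Step 5: which reading the text favours.**

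- *Last dose received:* Protocol 9.3.1 ties the collection period to each subject's own last dose. SAP 10.1.1 attributes an event to the most recent dose given before it, and SAP 10.1.3.4 counts onset from the last study vaccination. Amendment 1 changed the primary endpoint from last to second vaccination (Protocol Appendix C), so the sponsor treats the two terms as different. The safety windows still say last.
- *Calendar point:* Protocol 7.7.1, Table 22 and 11.10 equate the boundary with Day 90, Visit 3 or Month 3. Protocol 9.3.1 also names the Month 14 contact as the end of collection.

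The first reading is the literal one, but the text does not settle the matter.

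**Step 6: would a nominal Month 3 boundary alone cure it?** With one-dose subjects followed in the early window to Day 90, a stopping event stays early for any interval up to 90 days, which covers 49–83. At 180 days it does not. Stopping events on Days 91–180 would still be late while unrelated ones are early, which is 90/180 = 50% of the inter-dose days. A second element is needed.

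**The case against.** The strongest reply is that the selection exists on only one reading. If 30 days after the last vaccination means Month 3, a related SAE on Day 45 stays in the early table. This stands as a reason not to say that the tables certainly select against related events. It does not remove the need to choose a reading, because a programmer working from SAP 5.5.1 and 10.1.1 would probably use the last dose received.

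It is also true that the shares above are calendar days, not events. The documents give no expected number of one-dose subjects or stopping events. The shares would apply to events only if onsets were spread evenly between doses, and they would be smaller if onsets cluster in the first 30 days. The 180-day interval is an exceptional maximum. The safety comparisons are descriptive, and the primary endpoint and sample size are untouched.

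A reader might infer more than the documents support:

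- *That the events are lost.* They move to the late table. Related SAEs are also tabulated over the entire study (Protocol 11.10, SAP 5.5.1). SAP 5.5.2 lists all SAEs, and separately lists events leading to treatment discontinuation.
- *That the fatal-SAE tables have the same fault.* The SAP's fatal-SAE windows are cumulative from Day 1. A Day 45 death is in the Day 1 to Month 14 and entire-study windows on either reading, and in the first window by its Month 3 label.
- *That about 60 days of one-dose data fall in neither table.* The gap (60 + 365 = Day 425, against about Day 365) appears only if collection follows the nominal Month 14 while the tables follow the literal one year. Apply one reading to both and it closes.
- *That Protocol 7.5 is at fault.* The contraindication is not in question. The gap is in the analysis windows.

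**Conclusion.** The point holds as a conditional defect that should be corrected. On the literal reading, a vaccine-related SAE or unacceptable-risk pIMD that starts more than 30 days after dose 1 and before the planned dose 2 leaves the early table because of what it is. The stretch is Days 31–60 on the optimal schedule, up to Day 83 at the allowed limit, and longer under the special-circumstances interval. The sections that equate the boundary with Day 90 or Month 3 conflict with that reading and must be reconciled with it.

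The practical effect is on the early-window counts of related SAEs and pIMDs, and on their late-window counterparts. It matters most for pIMDs, because the unredacted text shows no whole-study pIMD table to compensate. The number of misplaced events cannot be derived from the documents and may be small. The conclusion assumes that last vaccination means last dose received, and that subjects stopped after dose 1 remain in follow-up.

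**What to change.** Amend SAP 5.5.1 as follows.

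(a) State that, for subjects without dose 2, the early window runs from Day 1 to nominal Month 3 and the late window from then to the Month 14 contact. Two-dose subjects keep their present windows.

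(b) For all subjects, show SAEs, related SAEs and pIMDs that start more than 30 days after dose 1 and before any dose 2 as a separate row. Membership then depends only on doses received by the time of onset, so the row is comparable at long dose intervals too. State where the row ends for a subject who never receives dose 2. Day 180, the longest interval in Protocol Table 11, would cover every case.

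(c) Add a cumulative Day 1 to Month 14 table for all SAEs and all pIMDs, as is already done for fatal SAEs.

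The cost is SAP wording and some table programming, with no new data and no change to any dosing rule. The drawbacks are minor. The window label departs slightly from the sponsor's usual one, and early windows still differ somewhat in length: 90 days for one-dose subjects, against 79 to 113 for two-dose subjects within the allowed intervals. Part (c) does not depend on that difference.
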